## 13. STATISTICAL CONSIDERATIONS

Further details of the proposed statistical analysis will be documented in the Statistical Analysis Plan (SAP), which will be finalised prior to any descriptive analysis of data pertaining to Study GWEP17005. Any deviations from the SAP will be described in the final clinical study report.

### 13.1. Sample Size, Power and Significance Levels

Up to 27 participants will be assigned to receive the study intervention in order to achieve 18 evaluable participants, which the Paediatric Investigational Plan for GWP42003-P considers sufficient to characterize PK in children < 2 years of age. Enrolment will be stratified to ensure that at least 5 participants each with LGS and DS (1 to < 2 years of age) and 8 participants with TSC (4 participants < 1 year of age and 4 participants aged 1 to < 2 years) are included in this study. The SAP will describe the definition of an evaluable participant in greater detail.

There will be no formal testing of statistical hypotheses in this study.

**Note:** Participants are considered “enrolled” when their parent(s)/LAR has/have signed the ICF (refer to [Section 9.1.1](#)).

### 13.2. Intermediate Analysis

Exploratory intermediate analyses may be conducted during the study to examine, for example, baseline data distribution, participant disposition, treatment exposure, or a subset of efficacy and safety outcomes, upon specific request. Results from these analyses may also support publication objectives (described elsewhere) or internal evaluation of trends. The justification and the details of any intermediate analysis will be documented in a separate SAP covering intermediate reporting.

### 13.3. Analysis Sets

#### Screening Analysis Set

All participants who are enrolled will be included. This analysis set will be used to describe administrative aspects of study enrolment, including reasons for screening failure.

#### Safety Analysis Set

All enrolled participants who receive at least 1 dose of GWP42003-P will be included. This analysis set will be used to estimate retention and all safety-related endpoints.

#### Efficacy Analysis Set

All enrolled participants who receive at least 1 dose of GWP42003-P and at least 1 post-baseline efficacy measurement (seizure diary or ITQOL-SF47). This analysis set will be used to estimate all efficacy-related endpoints.

- If warranted, a **Per-Protocol Analysis Set** may be additionally defined, in which participants with important protocol deviations that compromise efficacy assessments are excluded.

### **PK Analysis Set**

All enrolled participants who receive at least 1 dose of GWP42003-P, have at least 1 postdose PK measurement on Visit 9 or the EOT/ET visit, and have not experienced any intercurrent events that could impact exposure. Intercurrent events include an AE of vomiting that occurs within 2 times the median time to maximum plasma concentration ( $T_{max}$ ). This analysis set will be used for all PK-related endpoints.

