Visit Number	1	2 d	3 e	4 d	5	6 d	7	8 d	9	10	11 d , 12 d	13	14 d , 15 d	16	17 d , 18 d , 19 d	20	21	22 d	
Day	-2 8	-14	1	8	15	22	29	36	57	85	113 , 141	169	197, 225	253	281, 309, 337	365	375	403	
Window (days)	±3		+3		±3		±7												
Pharmacokinetics																			
PK			X	X		X		X								X			
 
At all indicated PK visits, samples are to be collected within 60 minutes prior to morning GWP42003-P dose (i.e., trough collection)
 
At Visit 9 and Visit 20, 3-hour and 6-hour postdose samples (≥ 2 hours between
 

Schedule of Activities																			
Study Period Visit	Screening/ Baseline Period (4 weeks)	Treatment Period (52 weeks)															End of Taper b	Safety Follow-up c	Notes
		Fixed		Flexible Dose Optimisation															
Visit Number	1	2 d	3 e	4 d	5	6 d	7	8 d	9	10	11 d , 12 d	13	14 d , 15 d	16	17 d , 18 d , 19 d	20	21	22 d	
Day	-2 8	-14	1	8	15	22	29	36	57	85	113 , 141	169	197, 225	253	281, 309, 337	365	375	403	
Window (days)	±3		+3		±3		±7												
																		each sampling time point) are also to be collected.	
																		
 
• Caregivers must record the participant's meals (timing and content) during the 24 hours prior to sample collection (Section 9.1.12.2).
 
• Doses adjustments should be avoided
 
	

Schedule of Activities																			
Study Period Visit	Screening/ Baseline Period (4 weeks)	Treatment Period (52 weeks)															End of Taper b	Safety Follow-up c	Notes
		Fixed		Flexible Dose Optimisation															
Visit Number	1	2 d	3 e	4 d	5	6 d	7	8 d	9	10	11 d , 12 d	13	14 d , 15 d	16	17 d , 18 d , 19 d	20	21	22 d	
Day	-2 8	-14	1	8	15	22	29	36	57	85	113 , 141	169	197, 225	253	281, 309, 337	365	375	403	
Window (days)	±3		+3		±3		±7												

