This statistical analysis plan (SAP) describes the planned analysis and reporting for Jazz Pharmaceuticals Research UK Limited “Jazz” protocol number GWEP17005 (An Open-label, Single-arm Study to Assess the Safety, Pharmacokinetics, and Efficacy of Adjunctive Cannabidiol Oral Solution (GWP42003-P) in Participants with Tuberous Sclerosis Complex (1 month to < 2 years of age), Dravet Syndrome (1 year to < 2 years of age), or Lennox-Gastaut Syndrome (1 year to < 2 years of age) who Experience Inadequately-controlled Seizures), dated 24-Jan-2024 version 6.0. Reference materials for this SAP include the protocol and the accompanying sample data collection documents. Operational aspects related to collection and timing of planned clinical assessments are not repeated in this SAP unless relevant to the planned analysis.

The structure and content of this SAP provides sufficient detail to meet the requirements identified by the Food and Drug Administration (FDA), European Medicines Agency (EMA), and International Conference on Harmonization (ICH) of Technical Requirements for Registration of Pharmaceuticals for Human Use: Guidance on Statistical Principles in Clinical Trials¹. All work planned and reported for this SAP will follow internationally accepted guidelines, published by the American Statistical Association² and the Royal Statistical Society³, for statistical practice.

The planned analyses identified in this SAP may be included in clinical study reports (CSRs), regulatory submissions, or future manuscripts.

The SAP described hereafter is *an a priori* plan. It will be submitted to file prior to any descriptive analysis of data pertaining to the Jazz Pharmaceuticals Research UK Limited “Jazz” (formerly GW) study GWEP17005.

In view of poor recruitment and retention, and the low likelihood of meeting planned enrollment, a decision was reached to terminate the study on 28 January 2025. Following database lock, an abbreviated CSR will be produced. This abbreviated SAP describes the analyses that will be undertaken to support CSR production.

2. Study Objectives and Endpoints

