2.2.2 Primary Endpoints - Exposure

- Trough, 3-hour, and 6-hour post dose plasma concentrations of GWP42003-P and its major metabolites following multiple doses of GWP42003-P.

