6.1 Statistical Definitions and Algorithms

6.1.1 Conventions for treatment/visit naming

In all tables and listings, the study visits will be referred to and labelled as per Table 1.

Table 1 Study Visits

Actual Visit	Visit Label	Phone Visit
Visit 1	Screening	
Visit 2: Baseline	Baseline	X
Visit 3: Day 1	Day 1 [§]	
Visit 4: Day 8	Day 8	X
Visit 5: Day 15	Day 15	
Visit 6: Day 22	Day 22	X
Visit 7: Day 29	Day 29	
Visit 8: Day 36	Day 36	X
Visit 9: Day 57	Day 57	
Visit 10: Day 85	Day 85	
Visit 11: Day 113	Day 113	X
Visit 12: Day 141	Day 141	X
Visit 13: Day 169	Day 169	
Visit 14: Day 197	Day 197	X
Visit 15: Day 225	Day 225	X
Visit 16: Day 253	Day 253	
Visit 17: Day 281	Day 281	X
Visit 18: Day 309	Day 309	X
Visit 19: Day 337	Day 337	X

Visit 20: Day 365	EOT/ET	
Visit 21: Day 375	End of Taper	
Visit 22: Day 403	Safety Follow-up ^f	X

[§] occurs 14 days (+ 3 days) after Visit 2, but not <28 days after Visit 1

^f Phone or clinic visit

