9.5.4 Plasma Concentrations of CBD and its Major Metabolites

At the indicated PK visits, a pre-dose sample will be collected within 60 minutes prior to the morning dose of the study intervention (*i.e.*, trough collection). The study intervention can then be administered during the visit once the pre-dose PK sample has been collected. At Visit 9 and Visit 20, additional PK samples will be collected at 3 and 6 hours after administration of the study intervention (each PK sampling time point will be separated by at least 2 hours).

Plasma concentrations of CBD and its major metabolites, 7-hydroxy-CBD (7-OH-CBD) and 7-carboxy-CBD (7-COOH-CBD), will be listed for all participants in the PK analysis set. Concentrations for each analyte will be summarized by the sample collection nominal timepoints for all participants in the PK analysis set.

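### Treated children with valid early troughs but no postdose sample at Visit 9 or EOT/ET are left out of every PK listing and summary, although trough is part of the primary exposure endpoint

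*Protocol*

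**What the plan says.** SAP 2.2.2 defines the primary exposure endpoint as "Trough, 3-hour, and 6-hour post dose plasma concentrations of GWP42003-P and its major metabolites following multiple doses of GWP42003-P". Troughs come from more visits than the postdose samples do. The PK notes in Protocol Appendix 1 say "At all indicated PK visits, samples are to be collected within 60 minutes" before the morning dose, while SAP 9.5.4 adds the later times at two visits only: "At Visit 9 and Visit 20, additional PK samples will be collected at 3 and 6 hours after administration of the study intervention".

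Entry to the PK set depends on those two visits. Protocol 13.3 and SAP 5 both require that a participant "have at least 1 postdose PK measurement on Visit 9 or the EOT/ET visit", besides at least one dose and no event that could affect exposure. Both make this the set for all PK endpoints.

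In SAP 9.5.4, plasma concentrations "will be listed for all participants in the PK analysis set". The summary has the same restriction: "Concentrations for each analyte will be summarized by the sample collection nominal timepoints for all participants in the PK analysis set".

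**The concern.** The endpoint counts a trough after repeated dosing as a primary observation in its own right, but the entry rule admits a child's troughs only if a different kind of sample exists at one of two visits. A child may have taken drug for weeks, given valid troughs and had no vomiting or dose change near any sample. That child is still outside the set if no Visit 9 or EOT/ET postdose sample was drawn.

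Whether that sample exists is unlikely to be unrelated to tolerability. A child stopped for safety may have no dose on the day of the ET visit, and then no 3-hour or 6-hour sample can be drawn. The trough description may therefore be selected on how well treatment was tolerated.

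The context adds weight. Protocol 13.1 justifies the sample size by PK characterisation in children under 2 years. Protocol 9.1.10 limits blood volumes tightly. SAP section 8 drops efficacy from the report. SAP section 1 says the study was closed "In view of poor recruitment and retention, and the low likelihood of meeting planned enrollment". Exposure is one of the main things left to report, and these samples have already been drawn.

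**Working it through.** **1. The plan's own count.** Protocol 13.1 gives 5 LGS + 5 DS + (4 + 4) TSC = 18, which matches the stated 18 evaluable participants. With up to 27 treated, the allowance is 27 - 18 = 9, or 1 - 18/27 = 33.3%. Neither document calls this a dropout rate. It is not a count of children outside the PK set either: SAP 5 makes a participant evaluable for the study if evaluable for at least one analysis set, and one dose is enough for the Safety set. So the 9 cannot serve as the number affected here.

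**2. Which visits give troughs.** The PK row of the Schedule of Activities is displaced in the text available. Read literally, its marks fall on Visits 3, 4, 6, 8 and a late visit. Visits 4, 6 and 8 are telephone visits (SAP Table 1), where blood cannot be drawn, and Visit 9 must be a PK visit. A one-column shift of those marks gives Visits 3, 5, 7, 9 and 20. This reading is an assumption. The Visit 3 sample precedes the first dose, so the multiple-dose troughs before Visit 9 are those at Visit 5 (Day 15) and Visit 7 (Day 29).

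**3. Tracing children through the rule** (no exposure-affecting event in any case).

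| Situation | In PK set? | Earlier troughs reported? |
|---|---|---|
| Visit 9 postdose sample taken | Yes | Yes |
| Leaves before Day 57, ET postdose sample taken | Yes | Yes |
| Leaves before Day 57, no ET visit | No | No |
| Leaves before Day 57, attends ET but no longer dosing, no postdose sample | No, if postdose means 3-hour or 6-hour | No |
| Stays past Day 57, no postdose sample at Visit 9 or EOT/ET | No | No |

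The second row holds because SAP Table 1 gives "Visit 20: Day 365" the label EOT/ET, and Visit 20 carries the trough, 3-hour and 6-hour samples. What decides inclusion is the missing sample, not the date of leaving.

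**4. Loss per child.** Analytes: CBD, 7-OH-CBD and 7-COOH-CBD, so 3. An early leaver outside the set loses up to 2 troughs x 3 analytes = 6 concentrations.

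**5. Number of children.** The documents give neither the number k who leave before Day 57 nor the share a of them with an ET postdose sample. The number excluded is k(1 - a). Purely as illustration:

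- k = 3: 3 excluded at a = 0, an average of 1.5 at a = 0.5, and 0 at a = 1. At 6 concentrations each, that is up to 18, 9 and 0.
- k = 6: 6, 3 and 0 excluded, or up to 36, 18 and 0 concentrations.

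**6. Do other provisions recover these data?** The optional subset analysis in SAP 5 covers participants with the exposure-affecting events (vomiting, recent dose adjustment), not those lacking a visit sample. The population PK analysis in Protocol 13.7.1.4 is reported separately. SAP 9.5.5 lists diary dosing and meals for the whole screening set, so an affected child's doses and meals would be listed without the concentrations they help to interpret.

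**The case against.** A reader might infer that the rule shuts out everyone who leaves before Day 57, so that exposure is described only in those who stayed. The documents do not support that. The rule names the ET visit as an alternative, and an early leaver sampled after dosing at ET enters the set with all earlier troughs, provided there is no excluding event. The request to attend ET is also firmer in places than the encouragement in Protocol 4.1: Protocol 10.1 and 12.6 say such participants should complete or proceed to an ET visit. Because the taper is planned to follow ET, many early leavers would still be dosing then. This stands, and it limits the gap to children without the sample.

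A reader might also infer that the lost troughs are the high ones. Nothing in the documents links exposure to early stopping. On the reading in step 2, the Day 15 trough is taken before any optional escalation, so it reflects the fixed titration and not an individually chosen dose. Selection is possible; its direction is unknown.

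Two further points stand in part. The population PK analysis is not stated to be limited to the PK set, so the data need not be lost to science, but they remain absent from this study's report. And postdose is not defined: if it means any sample after the first dose, an ET trough alone would qualify and the gap narrows, though it does not close for a child with no sample at either visit.

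Finally, this is a descriptive study with no hypothesis tests, reported in abbreviated form. That keeps the point modest. It does not justify leaving valid primary-endpoint observations out of even a listing.

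**Conclusion.** The point holds as a gap in reporting. A treated child with valid multiple-dose troughs but no postdose sample at Visit 9 or EOT/ET is in no PK listing or summary, and no other provision puts those troughs in the study report.

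Its size is up to 6 concentrations per affected early leaver, assuming the PK row reads Visits 3, 5, 7, 9 and 20. The number of such children is not given and may be 0. A study total should not be scaled from the 27 planned or from the difference between 27 and 18, because SAP 5 counts any dosed child as evaluable and the SAP itself regards planned enrolment as unlikely to be met. No figure in the documents is wrong on this point.

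The trough description may be selected on tolerability. The documents do not allow a statement about the direction or amount of any bias.

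**What to change.** Amend the SAP as follows.

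- **Sections 5 and 9.5.4, listing:** list all concentrations after the first dose for every treated participant with at least one reportable value at any PK visit.
- **Trough summaries:** use the same participants, still applying the vomiting and dose-adjustment exclusions.
- **3-hour and 6-hour summaries:** keep the Visit 9 or EOT/ET condition for these only, and state that postdose there means the 3-hour or 6-hour sample.
- **Section 9.6:** record the departure from Protocol 13.3. SAP 5 already differs from the protocol's PK set in its vomiting window and in adding a dose-adjustment exclusion, so both differences can be recorded together.

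No new samples or visits are needed. The cost is SAP wording and shell changes, and n will differ between trough and postdose rows. Showing n by visit and nominal time makes that plain.

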### **13.4. Protocol Deviations**

All protocol deviations will be listed.

### **13.5. General Considerations**

Unless stated otherwise, continuous variables will be summarised showing the number of non-missing values (n), mean, standard deviation or standard error, median, interquartile range, minimum and maximum. Categorical variables will be summarised showing the number and percentage of participants in each category.

Summaries will be presented by indication and overall, unless otherwise specified.

For clinic visit-based endpoints (unless otherwise specified), baseline is defined as the last record or measure collected prior to the first dose of GWP42003-P.

### **13.6. Accountability and Background Characteristics**

#### **13.6.1. Enrolment and Disposition**

All enrolled participants (screened, prematurely terminated study intervention, etc.) will be accounted for in the enrolment and disposition summary tables.

#### **13.6.2. Baseline and Demographic Characteristics**

Age, sex, race (as per local data protection laws in each specific country) and any other demographic or baseline characteristics will be summarised using appropriate summary statistics.

#### **13.6.3. Medical History**

Previous and current medical conditions (including details of TSC, LGS, or DS and other comorbid disorders) will be summarised by System Organ Class (SOC).

#### **13.6.4. Concomitant Medication**

Concomitant medications (including ASMs and antiseizure therapies) taken prior to and during the study will be summarised separately; details will be specified in the SAP.

#### **13.6.5. Treatment Compliance and Extent of Treatment Exposure**

Exposure to the study intervention overall and at each dose level, expressed in dosing days, in addition to treatment compliance will be summarised.

## **13.7. Endpoints and Statistical Methods**

### **13.7.1. Primary Safety and Pharmacokinetic Endpoints**

Analysis and reporting of the primary safety and PK endpoint parameters will include descriptive statistical summaries of each element at baseline and follow-up study visits where collection was performed.

#### **13.7.1.1. Adverse Events**

Adverse events will be collected as specified in [Section 9.1.1414](#), are defined in [Section 12.1](#), and will be coded according to the Medical Dictionary for Regulatory Activities dictionary.

Descriptive presentations of AEs will be given by preferred term and SOC for the safety analysis set. The number of participants reporting at least 1 AE will be provided. Adverse events will be summarised in terms of the number of participants with at least 1 event (N) and the percentage of participants with at least 1 event (%).

The following summaries will be produced as a minimum:

- All-causality AEs.
- Treatment-related AEs.
- All-causality AEs by maximal severity.
- All-causality serious AEs.
- Treatment-related serious AEs.
- The AEs reported as leading to permanent cessation of study intervention.
- Fatal AEs.

#### **13.7.1.2. Clinical Laboratory Data**

Clinical laboratory data will be summarised at screening/baseline and at each time point during the treatment period using appropriate summary statistics. Categorical shift tables will be presented, showing the numbers of participants with values outside the normal range. Change from baseline will also be summarised by visit.

#### **13.7.1.3. Vital Signs, 12-Lead Electrocardiogram, Physical Examination and Other Safety Data**

Vital signs, ECG, physical examination, and neurodevelopmental assessment data will be summarised, at screening/baseline and at each time point during the treatment period using appropriate summary statistics. Changes in the vital signs from baseline will also be summarised.

#### **13.7.1.4. Pharmacokinetics**

Plasma concentrations for CBD and its major metabolites (7-hydroxy-cannabidiol [7-OH-CBD] and 7-carboxy-cannabidiol [7-COOH-CBD]) will be summarised by nominal time, participant, and dose level. Pharmacokinetic data collected in this study will be combined with data from other studies to estimate PK parameters via a population PK analysis; results of this analysis will be reported separately.

### 13.7.2. Primary and Secondary Efficacy Endpoints

Analysis and reporting of the primary and secondary efficacy endpoints will include descriptive statistical summaries of seizure frequency, percent change from baseline, and percent change from baseline categories (i.e., increase or reduction, as specified in [Section 2](#)). Because GWP42003-P dose levels are not fixed during the study, summaries as well as 95% confidence intervals for percent change from baseline will be reported by indication and overall. Ancillary tables summarising efficacy endpoints by seizure type, based on indication, will also be provided.

#### 13.7.2.1. Total Countable Seizures

All measurements of total countable seizures (average per 28 days) will be determined as recorded by caregivers on seizure diaries at Week 12, every 4 weeks thereafter, and during the 4-week period prior to EOT.

##### Primary Efficacy Endpoint

The percentage change from baseline in indication-specific countable seizures\* will be summarised using descriptive statistics and including the lower and upper quartiles.

\*Indication-specific seizures are defined as follows:

- DS: Convulsive seizures, defined as tonic-clonic, tonic, clonic, or atonic.
- LGS: Drop seizures, defined as an attack or spell (atonic, tonic, or tonic-clonic) involving the entire body, trunk, or head that led or could have led to a fall, injury, slumping in a chair, or hitting the participant's head on a surface.
- TSC: Focal motor seizures without impairment of consciousness or awareness; focal seizures with impairment of consciousness or awareness; focal seizures evolving to bilateral generalised convulsive seizures and generalised seizures (tonic-clonic, tonic, clonic, or atonic) that are countable.

Additional seizure categories include other generalised or focal seizures (myoclonic, absence, focal non-motor, IS/ES, other) and SE (convulsive and non-convulsive seizures lasting 30 minutes or longer) that are **recognisable and countable**.

##### Secondary Efficacy Endpoints

- The number and percentage of participants considered treatment responders (i.e., with a  $\geq 50\%$  reduction in total countable seizures) will be summarised using descriptive statistics and including the lower and upper quartiles.
- The categorical percentage change from baseline to EOT in total countable seizures will be summarised, with categories defined as follows:
  - $> 25\%$  (increase)
  - $\geq 0\% \text{ to } \leq 25\%$  (increase)
  - $> -25\% \text{ to } < 0\%$  (reduction)
  - $> -50\% \text{ to } \leq -25\%$  (reduction)

- $>-75\%$  to  $\leq-50\%$  (reduction)
- $\leq-75\%$  (reduction)
- Seizure freedom, defined as 100% reduction from baseline in total countable seizures, will be summarised.

